### **Post-intervention phase:**

A KAP questionnaire administered before intervention will be used to assess the changes in knowledge, attitude, and practices of school adolescents in the post-intervention phase. Anthropometric measurement, micronutrient assessment, and physical assessment will also be done to assess the effectiveness of the intervention. Moreover, the checklist will also use to evaluate the changes in the School environment and WASH practices.

### **Phase III: Dissemination phase**

1. After the above-mentioned interventions, a one-day health camp will be arranged for all stakeholders (School children, school teachers, school health staff, and school management). The purpose of this camp is to summarize and reinforce all the concepts of the intervention phase of nutrition and WASH education and, deworming).
  - a. Puppet show
  - b. Games
  - c. Free health assessment for all (height, weight, physical assessment, blood pressure monitoring)
2. Outcome and recommendations of the study will be shared with policymakers and stakeholders for the improvement of the school system. The results of the study will be shared with all the stakeholders (adolescents, teachers, mothers/immediate caretakers). The study will be published in peer review journals, including other media channels. Findings will also share within advocacy groups of nutrition and WASH.

**Ethical consideration**

Study Approval will be obtained from the Aga Khan University Ethical Review Committee (ERC). Approval will also be sort from the participating school management in Gojra. Anonymity, confidentiality, and respect for human dignity are the main concerns in any of research addressing behaviors (Polit & Beck, 2008). Any identification information like name and personnel information will be replaced by codes to address anonymity issues. Confidentiality of the data will be ensured by keeping the data under safe custody, electronic files will also be password protected. Only the primary investigator will access the raw data and the research team members involved in data analysis. Respect for human dignity will be safeguarded by completely informing the participants about all aspects of the study including purpose, their rights including the right to withdraw from the study at any point, and all possible risks and benefits. This information will be communicated verbally as well as in writing in the form of consent /assent. For the adolescent's participation, assent will be obtained after taking permission from their parents / immediate caretaker. The trial will be conducted in compliance with the protocol, GCP, and the applicable regulatory requirement(s).

**Informed consent**

Consent will be taken in the language understood by the participants (Urdu, English, and local language). Informed assent will be taken before the start of the study by providing all the available information about the study. Upon agreement, consent participants will sign the form. For the adolescent's participation, assent will be obtained after taking permission from their parents / immediate caretaker.

**Sustainability of the project**

1. School teachers will be trained as master trainers to teach the nutrition and WASH module to 6-8 grade school-going adolescents.
2. Teachers should be trained in weight and height monitoring.
3. Encourage to change the behavior of adolescents and their parents to improve personal hygiene practices.
4. Findings of the study will be shared with the national nutrition program managers/administrators/policymakers.
5. Findings of the study will be shared with policymakers and suggested to inculcate the module as part of the curriculum.

**Expected outcome**

1. Adolescents' nutritional status will be improved i.e. BMI increase up to the normal range.
2. Knowledge, attitude, and practices regarding nutrition and WASH will be enhanced.
3. Adolescents will adopt WASH practices.
4. Overall, the health of adolescents and personal hygiene practices will be improved.

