## Introduction

Malnourishment is one of the grave public health issues and a significant cause of high morbidity and mortality among young Pakistani children. Several factors determine the high prevalence of malnutrition, which includes unsafe drinking water, poor sanitary conditions, lack of proper waste disposal facilities, poor health awareness, and poor nutrition and hygiene (Hirani, 2012). According to a report by the World Health Organization (WHO) published in 2017, malnutrition was categorized into three broad groups; “**undernutrition** (wasting, stunting, and underweight), **micronutrient related malnutrition** (deficiency or excess of micronutrients), **overweight, obesity and diet-related non-communicable diseases**” (Dat, 2018). According to another report by WHO, which was based on anthropometry, nutrition was classified as under and over-nutrition. According to this classification, **undernutrition** is divided into thinness, stunting, and underweight, while **overnutrition** is grouped into overweight and obesity. This classification of malnutrition was for children over five and adolescents. (De Onis, 2015).

At present, adolescents constitute the major proportion of all the age groups worldwide and 1.8 billion of the total world population consists of adolescents (between 10-19 years of age). Out of these, approximately 90 percent belong to Low and Middle-Income countries (LMICs) (Patton & Kabir, 201, Christian, 2018). The adolescent population was further divided into early and late adolescent by United Nations, the early adolescents age range between 10–14 years, and the late adolescents age group range between 15– 19 years (Christian, 2018).

In 2015, about 1.2 million adolescent deaths occurred globally (WHO,2017), 26 % of them in the South East Asian Region (WHO,2016). The leading causes of death in early adolescents include diarrheal diseases, intestinal infections and respiratory tract infections, and road traffic accidents (Dick, 2015). Malnutrition is the major contributing factor coupled with other causes of adolescent death (Reiner,2019). Globally, the main nutritional issues affecting

adolescents are undernutrition, anemia, and micronutrient deficiencies (Iron, Vitamin A, Zinc, and iodine,) (Shahid, 2009). Around 1.2 million adolescents in developing countries face serious nutritional challenges (Hossain, 2017 & Akhter, 2013).

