**Hypothesis**

$H_0$  = There will be no effect of nutrition education and WASH intervention on the prevalence of malnutrition among 6-8 grade school going adolescents.

$H_1$  = There will be a reduction in the prevalence of malnutrition among 6-8 grade school going adolescents through nutrition education and WASH practices.

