**Outcome of the study**

The main outcome is the reduction of malnutrition among school going early adolescents (6 to 8 grade) in a school setting that will be assessed through;

1. Body Mass Index
2. Micronutrients
3. Physical examination
4. Knowledge, attitude, and practices regarding nutrition and WASH

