**b. Dependent variables/Outcome of study**

1. Body Mass Index: All school going 6- 8 grade adolescents will undergo anthropometric measurements such as height, and weight (BMI). The measurement will be taken at baseline and end line by using WHO standard growth chart.
2. Micronutrients: Blood sample will be collected twice (baseline and end line) from a subset of 108 adolescents (54 intervention group,54 control group). The blood samples will help to assess the impact of intervention on micronutrient deficiencies (Iron, Zinc, Calcium, CBC, Vitamin D)
3. Physical examination: Physical examination like hair, skin, nail, eye (bitot spot), mouth (dental caries), and goiter will be assessed for micronutrient deficiencies at baseline and end line.
4. Knowledge, attitude, and practices regarding nutrition and WASH: a structured questionnaire will be used to collect data on nutrition and WASH-related indicators. The survey will be administered at baseline and end line. The indicator assessed will be adolescent health status and knowledge, attitude, and practices regarding nutrition and WASH practices.

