### **Activities of baseline assessment**

Activities	Purpose	Frequency
KAP survey	To know the KAP regarding nutrition and WASH	Baseline and end line
Anthropometric measurements	To identify the number of thin, underweight, Overweight, and Obese adolescents in 6-8 grade	Baseline and end line
Physical assessment	To identify the health status of adolescents	Baseline and end line

Monitoring CBC, Zinc, Calcium, and Vitamin D level	To identify the deficiency of micronutrients at baseline and improvement at the end line	Baseline & end line
Observations	To assess the practices related to major determinants of malnutrition i.e. nutrition, water, sanitation, and hygiene.	Baseline & end line

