### Data analysis plan

Quantitative variables will be described by means and standard deviations whereas median with interquartile range will be mentioned for qualitative variables. Frequencies and percentages will be calculated for the knowledge, attitude, and practices of adolescents regarding nutrition and WASH. The comparison between intervention and control at baseline and end line will be performed by using paired t-test and Chi-square. For the variables that are not normally distributed, a nonparametric test McNamara will be used. Binary logistic regression and multiple linear regression will be used to assess the effect of intervention. All the statistical analyses will be conducted using SPSS version 23. A p-value less than 0.05 will be considered statistically significant.

Descriptive	Inferential

 
• Mean, SD Normally distributed
 
• Median, interquartile range Skewed distribution
 
• Percentages and frequencies of knowledge, attitude, and practices
 
	
 
• Chi-Square-McNamara knowledge, attitude, and practices
 
• T- test paired Continuous variables
 
• Binary logistic regression and multiple linear regression
 
• Proportion changes - chi-square Observational checklist
 

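### Expected outcome counts only a BMI rise as improvement although overweight is malnutrition here, and the analysis plan lets raw BMI be tested as a within-arm mean change

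*Protocol*

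**What the plan says.** **Meaning of malnutrition.** In the Introduction, the classification for children over five and adolescents has an undernutrition side (thinness, stunting, underweight) and an overnutrition side, which "is grouped into overweight and obesity". The table under Activities of baseline assessment gives the purpose of anthropometry, at baseline and end line, as "To identify the number of thin, underweight, Overweight, and Obese adolescents in 6-8 grade".

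**Scale of the question.** The Hypothesis section states: "There will be a reduction in the prevalence of malnutrition among 6-8 grade school going adolescents". Outcome of the study states: "The main outcome is the reduction of malnutrition among school going early adolescents (6 to 8 grade"), assessed first through BMI. The RCT-phase sample size assumes 42% malnutrition in the control arm and a reduction of at least 6%.

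**Measurement.** Under Dependent variables/Outcome of study, pupils undergo "anthropometric measurements such as height, and weight (BMI") at both time points, using the WHO growth chart. No cut-off or z-score is given.

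**Meaning of improvement.** Expected outcome states that adolescents' "nutritional status will be improved i.e. BMI increase up to the normal range".

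**Analysis.** The RCT-phase Data analysis plan compares intervention and control by paired t-test and chi-square. Its table attaches the paired t-test to continuous variables, chi-square/McNemar to knowledge, attitude and practices (KAP), and chi-square for changes in proportions to the observation checklist. It adds: "Binary logistic regression and multiple linear regression will be used to assess the effect of intervention". No dependent variable is named for either regression.

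**The concern.** The only sentence that says what a better BMI looks like runs in one direction. An overweight or obese pupil cannot reach the normal range by a rise in BMI, so that sentence drops one side of the protocol's own definition of malnutrition.

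The analysis section does not repair this. Read literally, BMI is a continuous variable and goes to a paired t-test, while the categorical tests in the table belong to other outcomes. Two errors could follow:

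- The mean can stay put while both thinness and overweight fall, so a real benefit on the hypothesised scale is missed.
- BMI tends to rise with age in growing pupils, so a within-arm rise can be significant with no intervention effect and would look like the expected outcome.

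**Working it through.** **1. The texts side by side**

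| Place in the protocol | Scale | Ends of BMI covered |
|---|---|---|
| Introduction | categories | both |
| Activities of baseline assessment | counts in categories | both |
| Hypothesis; Outcome of the study; sample size | prevalence or reduction of malnutrition | not restricted |
| Expected outcome | rise in BMI | lower end only |
| Data analysis plan | paired t-test for continuous variables; no model tied to BMI | none stated |

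The contradiction needs no arithmetic.

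**2. The plan's own figure**

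The only relevant figure is the sample size: 180 per arm for 80% power at 42% control prevalence and a 6% reduction. It confirms that the trial was sized on prevalence. Read as 42% versus 36%, a pooled two-proportion calculation without clustering gives 21% power at 180 per arm (1037 per arm for 80%), so the stated power is not reproduced. That is a separate issue and does not decide this point.

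**3. Missing a fall at both ends**

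The split of the 42%, the BMI changes and the SD are assumptions.

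- Shift in mean = (share thin × gain) − (share overweight × loss).
- 25% thin gaining 1 kg/m2, 17% overweight losing 1: 0.25 × 1 − 0.17 × 1 = 0.08 kg/m2. At an SD of 3 this is 0.08/3 = 0.027 SD.
- 21% and 21%: 0.21 − 0.21 = 0.

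These shifts are small because the opposing changes were chosen to be equal. A second illustration avoids that choice. Take a normal z-score distribution with assumed cuts at −2 and +1. Let a = Φ⁻¹(share thin) and b = Φ⁻¹(1 − share overweight); then SD = 3/(b − a) and mean = −2 − a·SD. Cut both shares by the factor 36/42 and compare the means of two arms of 180 at two-sided 5%, ignoring clustering:

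| Thin / overweight | Shift in mean z | Power of a test on means |
|---|---|---|
| 21% / 21% | 0 | 5% (the test's own error rate) |
| 30% / 12% | +0.10 | 8% |
| 36% / 6% | +0.14 | 15% |
| 12% / 30% | −0.10 | 8%, opposite to the stated direction |

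A mean is a weak summary of this outcome even between arms.

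**4. Picking up growth**

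Growth g over the study and the SD of change are assumptions; n = 180 is the arm size.

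Paired t = g / (SD/√180), with √180 = 13.42.

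| g (kg/m2) | SD 1.0 | SD 1.5 |
|---|---|---|
| 0.20 | 2.68 | 1.79 |
| 0.45 | 6.04 | 4.02 |

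The two-sided 5% limit on 179 degrees of freedom is about 1.97, so 1.79 is not significant and the other three values are. Over g of 0.2 to 0.5 and SD of 0.8 to 1.5, the chance of a significant within-arm result with no intervention effect runs from 43% (g 0.2, SD 1.5) to over 99%.

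**The case against.** A reader might infer that the protocol defines improvement as a BMI increase and prescribes a continuous analysis of BMI. It does neither outright.

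- **The analysis of BMI is not assigned.** Binary logistic regression and chi-square are named, and with hypothesis and sample size on prevalence, a malnourished yes/no outcome is a natural reading. This stands: the continuous analysis is possible under the text, not stated by it.
- **Expected outcome is a narrative list.** It is not where endpoints are set, and its limit to the normal range means it speaks only of pupils below that range. It does not call a rise in an overweight pupil an improvement. This also stands; the fault is omission and conflict with other sections.
- **A reader might infer that the trial as a whole will credit growth as benefit.** The documents do not support that. Growth enters only through a within-arm test on raw BMI. The concurrent control arm in a between-arm model, or the WHO chart used as BMI-for-age, would largely remove it.
- **Cut-offs and derived variables are often left to a statistical analysis plan.** True, and their absence alone would be no finding. But the protocol makes its own choice here: it names a paired t-test for the comparison of intervention with control, gives it to continuous variables, and attaches the categorical tests in its table elsewhere. That choice, with the one-directional sentence, is what needs correcting.

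**Conclusion.** The point holds in limited form. Expected outcome conflicts with the Introduction, the baseline activities table and the prevalence hypothesis, because it omits overweight and obese pupils. The Data analysis plan leaves a literal route by which raw BMI is tested as a within-arm mean change, which can miss a fall at both ends or register growth.

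The contradiction rests on the text alone. The sizes do not: the thin/overweight split, the z-score cuts, the growth and the SDs are all assumed, and at the mildest combination the growth effect is not significant. They show direction and plausible order, not an expected bias. The point is worth correcting before analysis. It does not show that the planned analysis must fail, since the WHO chart and the logistic regression already in the plan would avoid both problems if tied to the outcome.

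**What to change.** 1. Reword Expected outcome so that improvement means BMI-for-age moving into the normal range from either side.
2. Make the malnutrition outcome the WHO BMI-for-age category at end line (thin, overweight or obese versus normal), with the cut-offs written down. Compare it between arms by the planned logistic regression, adjusted for baseline category.
3. Report thinness and overweight/obesity separately.
4. In any linear model use the BMI-for-age z-score, adjusted for baseline z-score, in place of raw BMI.
5. State that the within-arm paired t-test is not evidence of an intervention effect.

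The cost is small. Height, weight and the WHO chart are already planned at both time points. Age must be recorded among the demographic items, since the protocol mentions only demographic characteristics in general and sets eligibility by grade. The randomisation of four whole schools and the stated power are separate issues that this change does not resolve.

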**Timeline for study:**

After approval of the synopsis and ERC, the selection of schools will be carried out by June 2020, the first phase of data collection will be completed by July 2020, and intervention will be completed by March 2021. Summer and examination breaks will be excluded from the intervention plan. The timeline for the study will also be aligned with the school schedule.

